For Legacy studies (studies submitted prior to the Cayuse implementation), any modifications with the exception of research personnel should be listed here.
Yes

Additional Documents

√ No

Attach any additional documents (not listed in the sections to the left).

Preparing and Completing the Application

You do not have to finish the application in one sitting; the information will be saved and you may continue at a later time. As you complete the various sections of the application new sections relevant to the type of research being conducted will appear on the left-hand side; therefore, not all numbered sections may appear. You may go to another section using the menu on the left or the arrows at the bottom of each page. When adding attachments, each attachment button will allow you to add multiple documents and most common file types can be uploaded, including .pdf, .docx, and images.

Additional help information has been added throughout the form for guidance and clarity. That additional information can be found by clicking the question mark it the top-right corner of each section. You are strongly encouraged to use this feature! Once you have answered all required sections (indicated with a red asterisk), a green check mark will appear for that section (in the menu to the left). After all required sections are marked as complete, the option to submit the application will appear at the bottom left underneath all of the sections.

For more information about the TWU IRB submission process, IRB tracking, and Cayuse IRB Tasks, please refer to the TWU IRB Procedures, TWU IRB website, and Cayuse help features.

*required

TWU Campus

Note: If you are a student on a different campus than your faculty advisor, your faculty advisor's campus IRB will be the reviewing IRB.

Dallas

Denton

✓ Houston

Is this activity research?

*required

Does this research involve human subjects?

No

Please describe

*required Type c	of Project
Select	the type of project (Check all that apply).
✓	Thesis
	Professional paper
✓	Dissertation
	Class project
✓	Faculty research
✓	Pilot
	Other
*required Study	Review Category
Indicat	te the level of review for this study.
	Exempt
	Expedited
✓	Full
Drug, I	Devices, and Biologics
Will the	e study involve administering any of the following? Check all that apply.
✓	Drug/Supplements

Biolo	ogics
Devi	ces
None	e of the above
Funding So	purce
Have you a	lready received funding for this research project?
✓ Yes	

Hypertension (HTN) is one of the strongest risk factors for cardiovascular disease (CVD), and nearly half of all U.S. adults currently experience HTN (~47%, 122.4 million). Treatment of HTN typically involves a combination of pharmacotherapy and lifestyle modifications to control BP. However, despite the effectiveness of pharmacotherapy to treat HTN, incidence remains high due to poor adherence to medications, presence of resistant HTN and poor lifestyle habits. In 2015, a hybrid diet of the Mediterranean and DASH diet, termed the Mediterranean-DASH Intervention for Neurodegenerative Delay (MIND) diet was introduced. The MIND diet was developed after research findings from the Mediterranean and DASH diets suggested a positive correlation between specific foods and improved cognitive function. However, recent epidemiological data also suggests that high adherence to the MIND Diet eating pattern is associated with a 24% lower prevalence of HTN and lower systolic blood pressure as compared to low adherence to the diet. These preliminary data support the need for further clinical trials to investigate the feasibility and efficacy of the MIND diet to treat HTN.

To date, no study has examined the feasibility and efficacy of using the MIND diet to specifically treat HTN. Furthermore, given the additional benefit provided by exercise on BP reduction in patients with HTN, a lifestyle intervention that incorporates both the MIND diet and exercise training in patients with HTN is warranted.

Purpose/Objective of this study:

The overall objective is to assess the feasibility and efficacy of a 4-week novel diet and exercise intervention to improve blood pressure (BP), other cardiovascular disease (CVD) risk factors, and sleep in adults with hypertension and overweight/obesity.

*required

Research Questions/Hypotheses/Objectives

Provide the research question(s), study hypotheses and/or study objectives. Specific Aims & Hypotheses

1. To determine the feasibility of a 4-week novel lifestyle intervention consisting of a modified-MIND diet and high-intensity interval training (HIIT) in adults with hypertension and overweight/obesity.

Hypothesis: Adherence to 4-week lifestyle intervention will be high; with $\geq 75\%$ supervised exercise training visits completed and $\geq 75\%$ dietary compliance. We also hypothesize that study attrition will be low; with $\geq 75\%$ of enrolled participants completing our pilot study.

Yes

✓ No

Additional/ Other Inclusion Criteria

List any other inclusion criteria to be considered for participation in the study. Provide a rationale for all inclusion criteria listed.

Inclusion criteria include:

- Age 18 to 74 years old (Rationale: This is the best age range to target for BP reduction for primary prevention)
- Overweight or class I/II obesity (body mass index [BMI] = 25 39.9 kg/m2) (Rationale: Overweight or obesity is prevalent in over 60% of patients with hypertension in the US so translation is high here)
- Clinically diagnosed hypertension (by Physician or Nurse Practitioner) with or without current use of
 hypertensive medication (Rationale: To have the highest application and translation of these study
 findings to patients with hypertension we wanted to include patients with both treated (on
 medications) and untreated (not on medications) hypertension we appreciate this could be a
 potential limitation and will include "medication use" as as covariate in our final data analysis).
- Sedentary or physically inactive as defined as < 7,500 steps per day with physical activity monitor (Fitbit) (Rationale: We want to see the effects of this exercise intervention on individuals who are currently sedentary or inactive, not those who are already meeting the current ACSM guidelines for physical activity).
- Ambulatory (Rationale: In order to participate in exercise testing and exercise training the patients must be ambulatory)
- Able to read and speak English (Rationale: All participants must be able to read, speak, and understand English to participate in the study, as this is a requirement to follow diet and exercise instructions)
- Willingness to share medical record indicating diagnosis of HTN and current medication use

Additional/Other Exclusion Criteria

List any other exclusion criteria to be considered for participation. Provide a rationale for all exclusion criteria listed.

Exclusion criteria include:

- Current smoker (Rationale: May confound improvements in BP and other CVD risk factors and exercise tolerance)
- Severe/Class III obesity (BMI greater than or equal to 40 kg/m2) (Rationale: Severe/Class III obesity
 is associated with ambulatory issues that will limit participation in exercise testing and training)
- Height > 6 foot 6 inches (78 inches) (Rationale: Individuals taller than 6 foot 6 inches fall outside the region of interest (table) for DEXA images)
- Blood pressure ≥ 160/100 mm Hg (Contraindication to exercise testing and training)
- History of diagnosed cardiovascular diseases including myocardial infarction, atrial fibrillation, stroke, coronary artery disease, peripheral artery disease, or heart failure

- History of cancer, liver disease, kidney disease
- Diagnosis of type 1 or type 2 diabetes, or current use of insulin or metformin
- Diagnosed moderate or severe obstructive sleep apnea, use of CPAP, insomnia or history of any other sleep disorder (Rationale: The presence of major sleep disorders may mitigate intervention efficacy)
- Night shift and/or rotating shift worker (current or in the past 2 years) (Rationale: Night shift workers have known metabolic disturbances and their work schedule makes it difficult to participate in study testing and exercise training)
- Current use of sleep medications or sleep aids
- Excessive alcohol consumption defined as 8 or more alcoholic drinks per week in women and 15 or more alcoholic drinks per week in men (Rationale: Excessive alcohol intake may mitigate intervention efficacy)
- Any injury, joint issue, or medical condition that prevents participation in exercise testing and training
- A "yes" response to any questions on the Physical Activity Readiness Questionnaire (PAR-Q) (excluding Question 6 on use of BP medications)
- Pregnancy, breastfeeding
- Food allergy or lactose intolerance
- History of gastric bypass or other weight loss surgery
- Current use of dietary supplements or drugs for weight loss (including Ozempic and Mounjaro)
- Weight stable for the last 2 months (< 5 pounds body weight change)
- Current participation in exercise training (2 or more days per week of structured aerobic and resistance exercise training at a gym or at home)
- Current participation in a special diet to facilitate weight loss (Ketogenic Diet, Atkins, Paleo, Intermittent Fasting, etc.)
- Prior hospitalization for COVID-19 (Rationale: This is an added safety precaution to ensure patient safety as the long-term effects of COVID-19 hospitalization on exercise tolerance and CVD risk are unknown)
- Any medications or supplements that may alter study outcomes as determined by study PI during screening

Subject Recruitment

Will this study **ONLY** utilize secondary data (is this a retrospective study)?

Yes

✓ No

*required

Recruitment Process

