Participants who meet the inclusion/exclusion criteria for participation (as determined by Qualtrics pre-screening survey or pre-screening phone or Zoom call) will be asked to attend an in-person screening and consent visit at TWU – Houston. During the in-person screening visit, participants will complete a questionnaire regarding demographic and medical history, as well as the PAR-Q. Participants will also be asked to provide a copy of their medical records confirming the diagnosis of hypertension with or without current medication use. In addition, we will measure height, weight, and seated resting BP, to ensure that they meet the inclusion criteria for BMI and BP, respectively. If they pass screening, participants will undergo written informed consent to be enrolled in the study. At the end of this screening and consent visit, each participant will be provided with a physical activity/sleep monitor (Fitbit) to wear for 7 days. This is to ensure participants meet the criteria for sedentary or inactive – defined as < 7,500 steps per day. In addition, this Fitbit monitor also objectively measures sleep duration and quality (further details below). Finally, each participant will also be provided with an Ambulatory Blood Pressure Monitor to wear for the next 2 days.

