Approximately one week later, participants will return to our research lab at TWU Houston to undergo baseline testing. At this time, the research team will retrieve the ambulatory blood pressure monitor and Fitbit monitor from the participant to ensure compliance and eligibility, respectively. **We require a minimum of 70% of ambulatory blood pressure monitor recordings over a 24-hour period and an average daily step count of < 7,500 steps per day during the initial week of monitoring to qualify for the study.**All testing visits will be completed early in the morning following an overnight fast - water is permitted. Participants will be instructed not to consume any caffeine or alcohol, take any dietary supplements, or conduct vigorous exercise 24 hours prior to this visit. Thereafter, participants will undergo numerous physiological testing including seated resting BP, assessment of vascular function, anthropometry, venous blood draw, and maximal exercise testing to measure maximal oxygen uptake (VO2max). In addition, we will have participants complete surveys on quality of life and sleep quality, and current dietary intake. Following the completion of baseline testing, all participants will undergo a 4-week lifestyle intervention consisting of the MIND diet and supervised exercise training - HIIT. All study outcomes will be reassessed 48 to 96 h after the intervention is completed. All outcome assessments and exercise training will take place in the 10th floor research wing at TWU - Houston. The return of ambulatory blood pressure monitors is required after baseline and post-intervention testing. The Fitbit monitors must be returned to the study team immediately upon study completion at the final testing visit.

Procedures & Methodology

Private rooms are available for the PI to obtain informed written consent and collect other health-related data (medical history questionnaire and list of medications). All exercise testing and training for this study will take place in the Cardio Lab (Room 10131) located on the 10th floor research wing at TWU – Houston. The following assessments will be performed at baseline and post-intervention (in this order):

Ambulatory Blood Pressure Monitoring: Each participant will be given an Ambulatory Blood Pressure

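### No stable antihypertensive regimen is required before baseline, so blood pressure drift from a recent drug change cannot be separated from the effect of the intervention

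*Protocol*

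**What the plan says.** Under Additional/Other Inclusion Criteria the protocol admits "Clinically diagnosed hypertension (by Physician or Nurse Practitioner) with or without current use of" antihypertensive drugs. The stated reason is to make the findings apply to treated and untreated patients alike. The same bullet concedes that this is a "potential limitation and will include 'medication use' as as covariate in our final data analysis".

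The medical record is requested for diagnosis and present treatment only. The inclusion list asks for "Willingness to share medical record indicating diagnosis of HTN and current medication use", and under Study Design participants are to "provide a copy of their medical records confirming the diagnosis of hypertension with or without current medication use". The section on identifiable information limits the copy to material on the diagnosis and medication use.

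Two items under Additional/Other Exclusion Criteria bear on drugs:
- The PAR-Q exclusion carries an exemption, "excluding Question 6 on use of BP medications", so taking a blood pressure drug does not exclude anyone by that route.
- The last exclusion is "Any medications or supplements that may alter study outcomes as determined by study PI during screening". It names no drug class, look-back period or stability condition.

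On design, Study Design states that "all participants will undergo a 4-week lifestyle intervention consisting of the MIND diet and supervised exercise training - HIIT", and the trial is marked as non-randomized. Ambulatory pressure is recorded for 48 h before the intervention and for 48 h in its final week. The Statistics section tests pre-post change within the group by paired t-test, or by Wilcoxon signed-rank test if parametric assumptions fail.

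**The concern.** Someone who began a drug, or had a dose altered, days before screening meets every fixed criterion. Their pressure may still be moving when the baseline recording is made. With no comparator, whatever movement remains goes into the mean change on which Aim 2 rests.

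The planned analysis does not deal with this. A paired t-test takes no covariate. A covariate for medication use that distinguishes treated from untreated would code a recent starter and a long-stable patient alike. Its coding is not given and may be settled in the SAP, but nothing in the protocol promises to record the date of the last change, which any finer coding would need. Eligibility is fixed in the protocol, and no later analysis can restore a stable baseline that was never required.

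The protocol does recognise the principle elsewhere, with a two-month look-back for body weight: "Weight stable for the last 2 months (< 5 pounds body weight change". That item sits in the exclusion list, where read as written it would exclude weight-stable people, so it shows the idea but should not be copied as a template.

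**Working it through.** **Plan's own figures.** The protocol gives no effect size, standard deviation or power for blood pressure, so there is no figure of that kind to reproduce. The enrolment arithmetic is consistent: 9 completers of 12 enrolled is 9/12 = 75%, the stated completion target.

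**Time between recordings.** The first ambulatory recording follows the screening visit, the baseline visit comes about one week later, and the second recording falls in the last of four weeks. If the intervention starts promptly, the gap is about 1 + 3 to 1 + 4 weeks, or 4 to 5 weeks, in which a recent drug change could go on acting.

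**Shift in the mean change.** Inputs: n = 9 completers (Subject Enrollment); k participants with a recent change and d mmHg of residual drug-related change between recordings (both assumed; the protocol gives neither).

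Shift = k × d / n

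| k | d = 5 mmHg | d = 15 mmHg |
|---|---|---|
| 1 | 5/9 = 0.56 | 15/9 = 1.67 |
| 2 | 10/9 = 1.11 | 30/9 = 3.33 |

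The shift is a spurious fall after a start or increase, and an equal masking rise after a reduction or stop.

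**Effect on the test, in the favourable direction only.** A simulation of the paired t-test (two-sided alpha 0.05 as in Statistics, n = 9, no true intervention effect, 100,000 runs per scenario) used an assumed standard deviation of change of 6, 8 or 10 mmHg. It was run for d = 5 and d = 10 only. Ranges are across the three standard deviations.

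| k | Chance of a significant fall, d = 5 | Chance of a significant fall, d = 10 |
|---|---|---|
| 0 | about 2.5% | about 2.5% |
| 1 | 3.3 to 3.8% | 4.0 to 4.4% |
| 2 | 4.5 to 5.7% | 6.3 to 8.2% |
| 3 | 5.9 to 8.7% | 10.1 to 15.0% |

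The reference value is 2.5%, the lower tail of a two-sided 5% test. One affected participant makes little difference. Two or three begin to matter, depending on the size of the change.

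**The case against.** The strongest reply is that the discretionary exclusion already lets the investigator turn away a recent starter. It does allow that. But it neither directs attention to recent changes nor sets a standard for judging them, so it permits the safeguard without providing it.

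A reader might go further and infer that this exclusion contradicts the inclusion criteria, because antihypertensives plainly alter the main outcome and a literal reading would bar every treated patient. The documents do not support that. The rule is a case-by-case judgement at screening, the inclusion list deliberately admits treated patients and says why, and the PAR-Q item exempts blood pressure medication. Read together, these permit such treatment. A clarifying phrase is useful, but there is no contradiction.

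A reader might also infer that the bias must favour Aim 2. It need not: a recently reduced or stopped drug would push pressure up after baseline, and untreated patients, who may include recent stoppers, are eligible. Nothing in the protocol shows which direction would predominate.

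Three further points stand. The size rests wholly on assumptions and is small for one participant of nine. This is a pilot with feasibility as its first aim, and a single-arm pre-post design leaves other time-related explanations open as well. A pre-baseline stability rule also does nothing about drug changes during the four weeks.

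**Conclusion.** The concern holds as a gap in eligibility. No minimum period on an unchanged regimen is set, and in a single-arm pre-post comparison the resulting drift cannot be told apart from the intervention effect. The direction is unknown. Under the assumed residual change of 5 to 15 mmHg, the mean change among 9 completers shifts by 0.6 to 1.7 mmHg for one affected participant and by 1.1 to 3.3 mmHg for two. The omission is certain from the text; how often it would matter is not. The documents do not support saying that the blood pressure result would be invalid or necessarily inflated. The case for acting is that the remedy is cheap, acts on the main outcome, and cannot be supplied after enrolment.

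**What to change.** - Add an inclusion criterion that the antihypertensive regimen (drug and dose, or no drug) has been unchanged for a stated period before the baseline ambulatory recording. The investigators should choose the period.
- Ask that the medical record or medication list show the date of the last start or change. As now requested, the record covers diagnosis and current use and need not show this.
- Re-screen candidates with a recent change at a later date. No treatment is altered for the study.
- State that the discretionary medication exclusion does not apply to a stable antihypertensive regimen.

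The cost is a short amendment, an item on the screening checklist and slightly more record detail. A few candidates will be deferred or lost, which counts for something when at most 12 are to be enrolled.

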Prior to informed written consent and enrollment in the study, all interested participants will either complete an online Qualtrics Pre-screening survey or a virtual screening over the phone or via Zoom which includes:

• Inclusion/Exclusion Criteria Checklist: All inclusion and exclusion criteria are included in the online Qualtrics pre-screening survey and in a checklist as an attachment below (used for phone screenings).

Initial pre-screening will take place using the online Qualtrics Pre-screening survey or over the phone or via Zoom with the study study PI ([name]) or Co-PI ([name]). These pre-screening questions will be repeated in-person in a private room in the 10th floor research suite at the TWU-Houston campus to confirm. In order to limit the number of screen fails that occur in person, we have included the major inclusion criteria in the study flyer and will conduct initial study pre-screening over the phone or Zoom to save the participants and researchers time.

Attach any screening/eligibility testing documents. (If uploading a survey/questionnaire link, please also upload a pdf version for IRB records.)

Physical Activity Readiness Questionnaire_Non-Identifiable Version.pdf

Inclusion and Exclusion Criteria Checklist for Novel Lifestyle Study_CLEAN COPY.docx

Inclusion and Exclusion Criteria Checklist for Novel Lifestyle Study_REDLINE COPY.docx

Participant Follow-Up Email Script with Qualtrics Pre-Screening Survey.docx
Updated [name] & Zoellner_Qualtrics Pre-Screener Survey.pdf

No

*required

Will the subjects be told about the intent of the study prior to participating?

No

Research Procedures

Describe the research procedures in detail. (See the question mark on the right side for information that should be included here.)

Study Design

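### The weight-stability criterion is listed as an exclusion, so as written the trial turns away weight-stable adults and keeps only those whose weight moved by 5 lb or more in 2 months

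*Protocol*

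**What the plan says.** In the Protocol, the section Additional/Other Exclusion Criteria opens with "Exclusion criteria include" and runs as one list. Between the item on weight-loss agents and the item on current exercise training stands "Weight stable for the last 2 months (< 5 pounds body weight change". The item has no negation, no exception and no rationale.

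Two neighbouring exclusions deal with deliberate weight change: "Current use of dietary supplements or drugs for weight loss (including Ozempic and Mounjaro" and "Current participation in a special diet to facilitate weight loss (Ketogenic Diet, Atkins, Paleo, Intermittent Fasting, etc". Previous weight-loss surgery is also excluded.

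The inclusion list (Additional/Other Inclusion Criteria) covers age, BMI, diagnosed hypertension, low step count, ambulation and English, and ends with "Willingness to share medical record indicating diagnosis of HTN and current medication use". It has no weight-stability item.

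Under Eligibility Screening/Testing, the Protocol says of the pre-screening survey and the phone checklist: "All inclusion and exclusion criteria are included in the" survey and the checklist. The questions are then repeated in person.

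**The concern.** The item describes the people a study of this kind would want, but it is filed among the people to be refused. Applied literally, it selects participants whose weight is already changing.

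That is a particular problem in this design. The trial is non-randomized, every participant receives the diet and exercise programme, and the Statistics section tests pre-post change with a paired t-test or Wilcoxon signed-rank test. With no control arm, a weight trend that began before entry, or a rebound after recent loss or gain, enters the pre-post difference and is read as an effect of the intervention. The hypotheses name blood pressure, visceral fat and insulin sensitivity, all of which can plausibly move with weight. With up to 12 enrolled and at least 9 completers sought, a few drifting participants can shift the mean or widen its standard error noticeably.

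**Working it through.** The Protocol gives no figure to reproduce on this point. The main check is one of logic; the arithmetic only gives a sense of scale.

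**1. Who is in and who is out**

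Let Δ be the change in body weight over the last 2 months.

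| | Excluded on this item | Eligible on this item |
|---|---|---|
| As written | \|Δ\| < 5 lb | \|Δ\| ≥ 5 lb, gain or loss |
| With polarity reversed | \|Δ\| ≥ 5 lb | \|Δ\| < 5 lb |

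**2. Does anything else in the document correct it?**

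- The inclusion list has no item on weight stability.
- No other section states one.
- The exclusions for weight-loss agents, weight-loss diets and weight-loss surgery keep out people whose weight is being, or has been, deliberately changed. The weight-stability item read literally keeps out everyone else. Together they would leave only people whose weight has recently moved for some other reason, which serves no purpose stated in the Protocol.

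**3. Scale of the possible background drift**

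Inputs: 5 lb and 2 months (exclusion list); 4-week intervention (study objective). Assumptions not in the Protocol: the past rate of change continues, and blood pressure moves by 0.5 to 1.5 mmHg per kg.

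- 5 lb × 0.4536 kg/lb = 2.268 kg
- 2 months ≈ 8.7 weeks, so the intervention spans 4 / 8.7 = 0.46 of that period
- 2.268 kg × 0.46 = 1.04 kg over the intervention
- 1.04 × 0.5 = 0.52 mmHg; 1.04 × 1.5 = 1.56 mmHg

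Because 5 lb is the smallest change the literal rule admits, 1.04 kg is the least drift per participant if the trend continues.

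**4. From one participant to the group mean**

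If a share p of participants is losing weight and 1 − p is gaining, each at 1.04 kg per 4 weeks, the mean drift towards loss is (2p − 1) × 1.04 kg.

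- p = 0.5: 0 kg. No net bias, but added spread between participants.
- p = 6/9 (an illustrative split among 9 completers): (3/9) × 1.04 = 0.35 kg, or 0.17 to 0.52 mmHg.
- p = 1: 1.04 kg, or 0.52 to 1.56 mmHg.

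If gainers predominate the sign flips, and the drift hides benefit instead of mimicking it.

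**The case against.** The strongest reply is that this is an obvious slip. The text in brackets defines the desirable state, the surrounding items show the intent, and screening is carried out or confirmed by study staff, with a registered dietitian among the lead investigators. The survey, checklist and phone script are attachments that are not shown, and they may ask the question the right way round. Nothing in the Protocol shows that anyone was screened wrongly. The blood-pressure figure rests on an assumed slope and an assumed continuation of trend. Gainers and losers would partly cancel in a mean, and the exclusion of weight-loss drugs, weight-loss diets and regular exercise removes several causes of continuing loss, the direction that would imitate benefit. The study is also a small pilot whose first aim is feasibility.

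Much of this stands. The mmHg range is illustrative only, the direction of any net bias is unknown, and actual misapplication is not shown. None of it rescues the wording. Eligibility criteria are operative text, and the Protocol says all of them are carried into the survey and checklist, where a tick against an exclusion normally means rejection. If staff quietly read the item the other way, enrolment departs from the Protocol's text; if they follow it, the wrong people are enrolled. Feasibility may come first, but the second and third aims are efficacy aims tested at the 0.05 level.

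**Conclusion.** The concern holds. As written, the criterion excludes adults with less than 5 lb of weight change in 2 months and admits, on this item, only those with 5 lb or more. It conflicts with the evident purpose of the list it stands in, and nothing in the Protocol offsets it. That conclusion rests on the wording alone.

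Under literal application every enrolled participant would enter with recent weight change. The possible background effect is about 1.0 kg and 0.5 to 1.6 mmHg per participant at the 5 lb threshold, in either direction, with a net effect on the mean anywhere from zero to that size. This range depends on the two assumptions stated and is not an estimate of bias. The line must be corrected because it states the reverse of its apparent intent in a design that has no control arm to absorb the consequence.

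**What to change.** Either reword the exclusion so that it removes people who are *not* weight stable (a change of 5 pounds or more in the last 2 months), or move the present item unchanged to the inclusion list. One or the other is enough.

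Then check the inclusion/exclusion checklist, the Qualtrics survey (including any automatic rejection logic), the phone script and the in-person screening form, and make the polarity the same in all of them. If anyone has already been screened, review how this item was answered and acted on, both for those enrolled and for those turned away.

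The cost is one line in the Protocol, matching edits to the forms, and a short look back at screening records. No participants, visits or measurements are added.
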